A review of the current literature demonstrates silver sulfadiazine (SSD) to be the most frequently used dressing for burn wound treatment in many clinics nationwide.²⁸ The use of SSD is associated with once to twice daily painful dressing changes and wound exposure that "may lead to disruption of newly formed epithelium, wound colonization, subsequent wound infection and deepening of the burn".^{23, 28} One major benefit of the SCT is the reduction in

required dressing changes, as the soft cast can stay in place for 7-10 days while maintaining optimal hand or foot positioning. This eliminates the need for frequent painful dressing changes.

Occasionally, We have observed yeast infections when patients require serial casting and all have been treated with antibiotics. Other complications we have experienced include: occasional drying out of the adaptic gauze leading to a painful dressing removal and interruption of the newly epithelialized wound bed.

Mepitel Ag, a new soft silicone dressing produced by Molnlycke Health Care, combines Safetac technology with a silver compound to provide a broad spectrum of antimicrobial coverage. The safetac technology “protects the wound and the skin. It prevents an outer dressing from sticking to the wound, therefore minimizes trauma and pain”.¹⁵ The highly pliable nature and antimicrobial properties of the dressing make it an ideal alternative to TAO and SSD for the treatment of pediatric partial to deep partial thickness hand and foot burns. The silver compound lasts up to 8 days, while minimizing damage to the new epithelium and creating a moist wound environment. As Mepitel Ag is a relatively new product, there are currently no studies analyzing its efficacy and effectiveness when compared to other burn treatment methods.

The aim of this study is to compare Mepitel Ag to triple antibiotic ointment impregnated Adaptic gauze when used with the soft cast technique to assess overall time to healing, yeast infection rate and parents perception of pain level at time of dressing change on a scale of 1-10. The hypothesis is that Mepitel Ag in combination with the soft cast technique improves wound healing in pediatric partial to deep partial thickness hand and foot burns by decreasing the length of healing time, decreasing the risk of yeast infection, and decreasing pain associated with dressing changes.

III. Preliminary Studies/Progress Report:

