This is due to the fact that “soft silicone dressing have been shown to prevent trauma to the wound bed and periwound skin and have been described as ‘atraumatic’”.¹⁴ Other benefits of soft silicone dressings include the ability to conform to anatomical contours, a reduction in scar development, and reduced overall cost secondary to improved wound healing and need for less frequent dressing changes.¹⁴

Mepitel Ag, a hybrid type soft silicone dressing impregnated with a silver compound was recently approved for use in partial thickness burns and partial and full thickness grafts.¹⁵ This combination of soft silicone and silver provides a relatively pain free dressing with broad spectrum antibiotic coverage. The aim of this study is to demonstrate that Mepitel Ag in combination with a soft cast technique is a superior alternative to antibiotic ointment impregnated gauze and soft cast for the treatment of pediatric hand and foot burns due to decreased healing time, decreased patient pain and lower yeast infection rates.

IV. Research Methods

A. Outcome Measure(s):

Primary outcomes utilized in this study include overall wound outcome, measured in length of days to re-epithelialization or need for surgical intervention, clinical assessment and wound progression photographs. Secondary outcomes include number of patients requiring surgical debridement, presence of infection based on odor, rash, deep red appearance or puritis. These wounds will not be cultured, patient pain level with dressing change based on the FLACC (Face, Legs, Activity, Cry, Consolability) scale, parents perceived level of pain, pain level at home based on family reported pain and pain medication use. We will also assess cost effectiveness of dressings including the number of clinic visits, number of soft casts, and the cost and amount of dressings used over the course of treatment.

B. Description of Population to be Enrolled:

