A member of the nursing team will also complete a questionnaire at each follow up visit to indicate pain level with dressing change based on the FLACC scale, parents perceived level of pain during dressing change, parental reported pain level at home, use of home pain medications, type of home pain medication- narcotic vs non-narcotic, clinical assessment of yeast rash including odor, visible rash, use of fluconazole, ease of dressing application, and amount and type of product used in dressing change.

D. Description, Risks and Justification of Procedures and Data Collection Tools:

A photography release will be distributed and signed by parent at initial visit.

Anursing questionnaire will be completed by nursing staff at each follow up appointment.

Local wound care including cleansing, wound measurement and dressing change will be performed by burn team including nursing staff and occupational and physical therapists. Although punch biopsy with histological analysis is considered the 'gold standard' in assessing burn wound depth, it is invasive and time consuming.¹⁸ Clinical assessment remains the most frequent and rapid method.¹⁸ Due to the time sensitive nature of the proposed trial and in order to avoid delaying wound care and initial dressing application, a 10 point clinical assessment scale has been created, as listed above for use in determining initial burn wound severity. Patient wound depth will be clinically determined by the average of the scores from the provider and the burn nurse.

The wound will also be assessed by the provider and nurse on subsequent visits using the following scoring tool: 1=0% healed, 2=20% healed; 3=40% healed; 4=60% healed; 5=80% healed; 6=100% healed. This will be established by provider and burn nurse examination of the wound. This will be recorded in RedCap.

The overall risk for this study is minimal, with no foreseen adverse reactions. The risk of a silver allergy or adverse reaction to silicone is very rare.

E. Potential Scientific Problems:

Limitations to the proposed study design include varying diagnostic opinions between provider and burn nurse for the determination of superficial vs deep partial thickness burn wounds based on clinical assessment, provider or nurse bias based on dressing preference, and possible uneven trial groups.

F. Data Analysis Plan:

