Analysis Plan: Demographic and clinical characteristics will be summarized and compared between the two treatment groups using chi-squared and two-sample t-tests for categorical and continuous data, respectively. For analysis of the primary outcome, time to wound healing, we will use Kaplan-Meier curves, the log-rank test and a Cox proportional hazards model to determine the difference in days to re-epithelialization between the TAO and Mepitel Ag soft cast methods. Patients that require surgical intervention will be censored at the time of surgery. Logistic regression will be used to analyze the secondary outcomes, need for surgical debridement and occurrence of yeast infection. Pain level outcomes and pain medication use will be compared using two-sample t-tests and chi-squared tests. Cost effectiveness outcomes will also be analyzed.

1. Sample size: A statistical power analysis was performed to estimate power, based on results reported in A Soft casting Technique to Manage Pediatric Hand Burns: Less Pain, Greater Gain.²² Considering the simplest between group comparison and assuming a standard deviation of 0.3, alpha of 0.05 and 50 subjects per group there is over 90% power to detect a difference of 2 days between the treatment groups. Thus, we expect that our proposed sample size of 100 burns will be adequate for the main objective of this study.

G. Summarize Knowledge to be Gained:

To demonstrate that Mepitel Ag in combination with a soft cast technique improves wound healing in pediatric partial to deep partial thickness hand and foot burns by decreasing the length of healing time, decreasing the risk of yeast infection, and decreasing pain associated with dressing changes.

H. References:

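### The general infection outcome in IV.A is not matched by the visit questionnaire or the analysis, which cover yeast only, and no field is described for dressing reactions or cast-related skin injury

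*Combined protocol and SAP*

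**What the plan says.** All references are to the combined protocol and SAP.

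- **IV.A Outcome Measure(s).** One secondary outcome is "presence of infection based on odor, rash, deep red appearance or puritis. These wounds will not be cultured". It is not limited to yeast. Surgical debridement, FLACC pain, parent-perceived pain, pain at home and pain medication are also listed.
- **IV.C Study Design and Research Methods, nursing questionnaire.** At each follow-up visit the infection items are "clinical assessment of yeast rash including odor, visible rash, use of fluconazole". The questionnaire also serves "to indicate pain level with dressing change based on the FLACC scale, parents perceived level of pain during dressing change", and it covers home pain, home pain medication and its type, ease of application and products used.
- **IV.D Description, Risks and Justification.** "The overall risk for this study is minimal, with no foreseen adverse reactions". The next sentence reads: "The risk of a silver allergy or adverse reaction to silicone is very rare".
- **IV.F Data Analysis Plan.** Logistic regression is planned for "need for surgical debridement and occurrence of yeast infection". Pain and pain medication are compared with t-tests and chi-squared tests. No adverse event definition or safety table is described.
- **Background and Significance.** Mepitel Ag "combines Safetac technology with a silver compound to provide a broad spectrum of antimicrobial coverage". The same section reports complications already seen with the current technique: yeast infections during serial casting, gauze that dries out, painful removal, and disturbance of new epithelium.

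**The concern.** The trial compares two antimicrobial contact layers that stay under a closed cast for days, in children from 31 days of age. The Background says that no studies yet compare this product with other burn treatments. An outcome that covers infection in general should have a data source and an analysis of the same breadth. Here the outcome is general, while both the form and the analysis are specific to yeast.

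Three things are at stake:

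- The infection outcome in IV.A cannot be put together from what is collected, and analysts cannot fully recover it later.
- Lower yeast risk is one of the hypothesised benefits. Rash is a yeast item on the form, but it can also reflect a contact reaction. With no separate field, a dressing reaction could be counted as yeast, which would blur that comparison in either direction.
- Non-yeast infection, dressing reactions and cast-related skin injury would not be compared between arms in any systematic way.

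**Working it through.** **1. The three sections side by side**

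| Sign or event | Outcome (IV.A) | Questionnaire (IV.C) | Analysis (IV.F) |
|---|---|---|---|
| Odor | Yes, as infection | Yes, under yeast rash | Only as yeast infection |
| Rash | Yes, as infection | Yes, under yeast rash | Only as yeast infection |
| Deep red appearance | Yes, as infection | Not described | None |
| Pruritus | Yes, as infection | Not described | None |
| Non-yeast infection | Covered by the general wording, not separated | Not described | None |
| Silver, silicone or contact reaction | No | Not described | None |
| Cast or pressure injury to skin | No | Not described | None |
| Surgical debridement | Yes | Not listed | Logistic regression |
| Pain, pain medication | Yes | Yes | t-test, chi-squared |

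Two of the four infection signs have no described field, and the other two are recorded only as signs of yeast. Because wounds are not cultured, clinical signs and treatment given are the only means of separating causes. The one antimicrobial on the form is fluconazole, yet the Background says that the yeast infections seen so far were treated with antibiotics. An antibiotic field without an indication would therefore not isolate bacterial infection.

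**2. The plan's own figure**

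IV.F gives over 90% power for 2 days, with SD 0.3, alpha 0.05 and 50 per group. The standard error is 0.3 × √(2/50) = 0.06 and 2/0.06 = 33.3, so power is essentially 100% and the statement is met. It has no bearing on harms. Only the 50 per group is carried forward.

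**3. What a harms table could show at 50 per arm**

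The documents give no event rates, so the rates below are assumptions.

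- Zero events in 50, exact one-sided 95% upper bound: 1 − 0.05^(1/50) = 5.8%. Two-sided: 1 − 0.025^(1/50) = 7.1%.
- Chance of at least one event in an arm, 1 − (1 − p)^50: 39% at p = 1%, 64% at 2%, 92% at 5%.
- Five events against none, two-sided Fisher: 2 × C(50,5)/C(100,5) = 2 × 2,118,760/75,287,520 = 0.056.
- Two-sided power at alpha 0.05, Φ[(d − 1.96·SE₀)/SE₁], where d is the difference in rates, SE₀ is pooled and SE₁ unpooled. For 5% vs 10%: (0.05 − 1.96 × 0.0527)/0.0524 = −1.015, giving 15%. The same formula gives 38% for 5% vs 15% and 62% for 5% vs 20%.

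**4. Burns, not children**

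IV.B makes each injured extremity a separate data point, and IV.F counts 100 burns. With bilateral injuries there are fewer than 50 children per arm and the per-child bound is wider. For illustration, if 50 burns came from 40 children (an assumption), the bound would be 1 − 0.05^(1/40) = 7.2%.

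**The case against.** The strongest reply is that the plan is not silent on harm. IV.A names infection without limiting it to yeast, so infection is not wholly uncounted. Debridement, yeast infection, pain and pain medication are compared by arm, healing is scored and photographs are taken at each visit. The cast is common to both arms and is current practice, so it is a weak source of a difference between arms. The superiority aim concerns healing time, pain and yeast infection, and claims no safety advantage. The risk sentence is followed at once by the two rare reactions, and excluding known silver or silicone allergy lowers that risk and does not contradict the sentence. The disturbance of new epithelium was seen with the existing gauze, which is the control dressing. Finally, the questionnaire is described in prose and the form itself is not shown.

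Most of this stands, and it limits the point. It does not close the gap. IV.A's outcome still needs two signs that the described form lacks, and IV.F still narrows the analysis to yeast. Photographs cannot record pruritus, odor or treatment started. A cast shared by both arms still leaves the frequency of skin injury undescribed. Since the form is not shown, the correct statement is that no field is described, not that none exists.

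**Conclusion.** The point holds as a mismatch between IV.A, IV.C and IV.F, together with the absence of any described field for non-yeast infection, dressing reaction or cast-related skin injury. Correcting it is a cheap improvement that serves both safety and one of the trial's own outcomes.

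A reader might infer that the trial has no safety data, or that bacterial infection is not counted at all. The documents do not support this: several harm-related outcomes are compared by arm, and IV.A's wording can include bacterial infection, although it is not separately identified. A reader might also infer that the trial would declare superiority in the face of harm. That is speculation, since harm could lengthen healing, raise pain or lead to surgery, and all of these are outcomes. The risk sentence is loose beside the complications that the Background reports, but it needs only a wording edit.

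The size is modest. At 50 burns per arm, a zero count leaves rates up to about 5.8% open (more per child), and even 5 versus 0 does not reach 0.05 on a two-sided Fisher test. The value lies in description. The conclusion assumes that the questionnaire holds what IV.C lists; consent pages are not available, so any risk wording there could not be checked.

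**What to change.** 1. Reconcile IV.A, IV.C and IV.F: state whether the outcome is any infection, yeast infection, or both, and give each one its signs, its field and its analysis.
2. Add to the existing questionnaire, each as yes/no with a date: deep red appearance; pruritus; suspected non-yeast wound infection; systemic antimicrobial started, with its indication; allergic or contact skin reaction; and cast or pressure injury as its own field. Do not merge the last with unplanned visits, because a combined field could not be interpreted.
3. In IV.F, add one descriptive table of counts by arm, per child, with exact confidence intervals and no formal test.
4. Reword the risk sentence in IV.D so that it agrees with the reactions named directly after it and the complications reported in the Background.

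The cost is a form edit, about a minute of nurse time per visit and one extra table. Sample size is unaffected.

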Patients to be included in this study will be all Children's Hospital Colorado burn patients between the ages of 31 days and 18 years with newly diagnosed partial to deep partial or full thickness hand or foot burns, including bilateral or unilateral injury. Each injured extremity will serve as a separate data point. Exclusions include age > 18 years at start of study, silver allergy, silicone allergy, electrical or chemical burn, past medical history of immunodeficiency disorders such as diabetes mellitus, AIDs, or HIV, pregnant women, prisoners children under the protection of the department of human services, and the decisionally challenged.

C. Study Design and Research Methods

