New burn clinic patients identified with a partial to deep partial or full thickness hand or foot burn will be randomized into either the Mepitel Ag group or the control group on their first clinic visit based on burn wound severity and age using RedCap. The randomization scheme in RedCap will be independently created by a statistician. Parental consent and or patient assent will be obtained prior to initial dressing. Burn severity will be clinically determined by one provider and one burn nurse during initial exam based on a 10 point burn severity classification scale in regards to the following parameters: 1) Superficial first degree- wound appears pink or red, involves epidermis only, no blisters present, dry; 2) Second degree, superficial partial thickness- burn involves epidermis + dermis, red or bright pink in color with blisters and or swelling, blanches, moist appearing; 3) Second degree, majority superficial partial thickness, minority superficial- burn involves majority ($\geq 66\%$) superficial partial thickness, epidermis + dermis, red or bright pink in color with blisters and or swelling, blanches, moist appearing, minority ($\sim 33\%$ or less) superficial first degree with areas of redness but no blistering; 4) Second degree, majority partial thickness, minority deep partial thickness- majority of burn ($\geq 66\%$) epidermis + dermis, red or bright pink in color, moist, less than half of burn ($\sim 33\%$ or less) is deep with pale pink-white areas, may or may not have a marbled or mosaic appearance; 5) Second degree, deep partial thickness- involves epidermis + dermis, pale pink to white in color, may have thin white moist eschar, may or may not have a marbled or mosaic type appearance, moist; 6) Second degree, majority deep partial thickness, minority superficial partial thickness- minority of burn ($\sim 33\%$ or less) involves epidermis + dermis, red or bright pink in color, moist, majority ($\geq 66\%$) of burn is deep with pale pink-white areas having a marbled or mosaic appearance, may or may not have thin white moist eschar, skin buds may or may not be present; 7) Second degree, deep partial thickness with areas of full thickness- majority of burn ($\geq 66\%$) involves epidermis + dermis, pale pink to white in color, may have thin white moist eschar, may or may not have a marbled or mosaic type appearance, moist, skin buds may or may not be present, minority of burn ($\sim 33\%$ or less) demonstrates thin to thick area of eschar white, brown or black in color, may need skin graft to heal; 8) Third degree full thickness with minority partial thickness- majority of burn ($\geq 66\%$) involves entire dermis + epidermis, thin to thick eschar that is white, brown or black in color, dry appearing, minority of burn ($\sim 33\%$ or less) is pink or red and moist, with blisters and or swelling, blanches; 9) Third degree full thickness- involves entire dermis + epidermis, thin to thick eschar that is white,

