
brown or black in color, dry appearing; 10) Fourth degree- third degree + muscle and or bone involvement. The provider and burn nurse will each give the patient a number and the severity will be determined based on the average of the 2 numbers. Any patient given a number 2, 3 or 4, will be placed into the "partial thickness" category, any patient given a 5, 6, or 7 will be placed into the "deep partial thickness" category, and lastly, any patient given an 8 or 9 will be placed into the "full thickness" category for burn severity.

Patients will be randomized into one of two groups, Mepitel Ag or standard TAO, using RedCap and based on a random clinical trial excel spread sheet balanced by burn severity. A statistician will provide a randomization scheme for investigators to follow. Photographs will be taken prior to dressing application at the initial visit and each subsequent visit. ~~Patient wounds will be dressed in either Mepitel Ag, kling or kerlex, cast padding, gypsoma plaster, soft cast material and coban for up to 21 days or until complete re-epithelialization of the wound occurs or unless surgery is indicated; the control, standard dressing of Triple Antibiotic Ointment impregnated adaptic gauze, kling or kerlex, cast padding, gypsoma plaster, soft cast material and coban for 10-14 days, or Nystatin impregnated adaptic, kling or kerlex, cast padding, gypsoma plaster, soft cast material and coban for 8-21 days or until complete re-epithelialization of the wound occurs or surgery is indicated. The SCT is applied by Occupational and Physical trained in casting and positioning. The soft cast provides optimal positioning while eliminating friction on the burn area. Dressing changes will occur every 3-10 days and will be determined by the provider, based on burn wound severity. Upon each return clinic visit, the patient will have their wound severity assessed by the following scoring system: 1=0% healed, 2=20% healed; 3=40% healed; 4=60% healed; 5=80% healed; 6=100% healed. This will be established by provider and burn nurse examination of the wound. This will be recorded in RedCap:_____~~

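### Allocation is balanced on burn severity, but the primary log-rank test is unstratified as written and the Cox model names no covariates, which costs power if severity predicts healing

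*Combined protocol and SAP*

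**What the plan says.** Section IV.C describes allocation twice. Its opening says patients are randomised "on their first clinic visit based on burn wound severity and age using RedCap". After the severity scale, it says the scheme is "based on a random clinical trial excel spread sheet balanced by burn severity", and age is not mentioned. The provider and the burn nurse each score the burn from 1 to 10, and the average sets severity. Scores 2 to 4 are partial thickness, 5 to 7 deep partial, and 8 or 9 full thickness.

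Section IV.F, the only analysis plan, says that for time to healing "we will use Kaplan-Meier curves, the log-rank test and a Cox proportional hazards model" to compare the two dressings, with censoring at surgery. It names no strata and no covariate list. Its baseline chi-squared and t-tests do not bring severity into the primary comparison. The sample-size paragraph claims over 90% power for a 2-day difference, "assuming a standard deviation of 0.3, alpha of 0.05 and 50 subjects per group", from a simple two-group comparison.

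On the unit of analysis, Section IV.B says "Each injured extremity will serve as a separate data point", whereas Section IV.C says "Patients will be randomized into one of two groups, Mepitel Ag or standard TAO".

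**The concern.** Balancing the arms on a prognostic factor removes that factor's contribution to the chance difference between arms. An unstratified log-rank test still carries the factor's variation in its reference distribution. It therefore rejects too rarely under the null and misses real effects more often than a test stratified by the same factor.

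The plan itself suggests that severity matters. It is an allocation factor, enrolment runs from partial to full thickness, and the scale notes that grade 7 burns may need a graft. If severity does shift healing time, the analysis gives up precision that the allocation scheme was set up to provide, in a trial of only 100 burns. For the Cox model the covariates are simply unstated, so whether to adjust could be decided after the data are seen.

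**Working it through.** **1. The plan's own figure.** Inputs from Section IV.F: 50 per group, difference 2 days, SD 0.3, alpha 0.05 (taken as two-sided). The difference is 2 / 0.3 = 6.7 SDs, so power is effectively 100% and the claim of over 90% holds as an inequality. By the normal formula, the largest SD that still gives 90% power is 2 / [(1.960 + 1.282) × √(2/50)] = 2 / (3.242 × 0.2) = 3.08 days; the t-test gives 3.05. An SD of about 3 days is therefore a natural reference point, but it is an assumption.

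**2. Method.** Each simulation had 100 burns, permuted blocks of 4 within severity category, and log-rank tests at two-sided 5%. Healing times were normal with a 2-day benefit, except in the Weibull rows. The severity effects, case mix, block size and censoring pattern are all assumed, because the documents give none of them. The main two-category runs used 4,000 replicates per scenario (Monte Carlo SE at most 0.8 points) and the Weibull runs 3,000.

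**3. Power, unstratified against severity-stratified log-rank.**

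| Assumed scenario | Unstratified | Stratified | Loss (points) |
|---|---|---|---|
| Stated SD 0.3, taken as the total SD | 100% | 100% | 0 |
| Total SD 3, two categories 50/50, severity explains 0% of variance | 86% | 86% | 0 |
| same, 20% | 87% | 91% | 4 |
| same, 40% | 90% | 97% | 7 |
| same, 60% | 95% | 100% | 5 |
| Within-category SD 3, means 12/14 days | 83% | 85% | 2 |
| Within-category SD 3, means 11/16 days | 69% | 85% | 16 |
| Weibull, mix 50/35/15, healing HR 1.8, censored at day 28, medians 12/12/12 | 82% | 80% | −2 |
| same, medians 10/14/18 | 67% | 80% | 13 |
| same, medians 9/15/24 | 45% | 78% | 33 |
| Within-category SD 3, mix 45/40/15, means 11/15/20, all heal | 51% | 85% | 34 |
| same, with two assumed patterns of surgical censoring | 56%, 51% | 80%, 73% | 24, 22 |

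A further three-category run with surgical censoring gave 49% against 82%, a loss of 33 points.

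**4. Why the rows differ so much.** In the 0 to 60% rows the total SD is held at 3. A stronger severity effect then shrinks the within-category SD, and both tests approach 100%. In the other normal-model rows the within-category SD is held at 3, so severity adds to the total. For means 11/16 the total SD is √(9 + 2.5²) = 3.9. For 11/15/20 the mean is 0.45×11 + 0.40×15 + 0.15×20 = 13.95, the between-category variance is 9.85, and the total SD is √(9 + 9.85) = 4.3. The documents do not show which picture applies.

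**5. Type I error from this omission alone.** In the total-SD-3 runs, the unstratified test fell from 4.8% to 1.1% as severity went from explaining 0 to 60% of variance; the stratified test stayed at 4.9 to 5.8%. In the Weibull runs the figures were 5.1%, 3.2% and 1.4% unstratified against 4.9%, 5.1% and 5.5% stratified. The error is conservative, never inflated.

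**6. Visit-based dating.** Healing is scored at clinic visits, and Section II says "the soft cast can stay in place for 7-10 days". Dating healing to visits 7 to 10 days apart lowers both tests in the total-SD-3 scenarios, to 58–73% unstratified and 58–78% stratified. The direction does not change.

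**7. Interaction with limb clustering.** With 30% of children bilateral and a strong shared effect within child (both assumed), treating limbs as independent gave type I error of 6.6% unstratified and 8.2% stratified with moderate severity effects. With no severity effect the figures were 7.5% and 6.9%. Where severity is prognostic, the conservatism was hiding part of the clustering inflation.

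**The case against.** The strongest reply is that nothing here biases the result, type I error is not inflated by this omission, and at the plan's stated SD the loss is nil. The size rests entirely on assumed healing times and case mix. All of that stands. It makes this a request to prespecify, not a flaw that invalidates the trial. The stated SD gives limited comfort, because it makes the target difference 6.7 SDs and leaves the realistic margin unestablished.

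Several stronger readings are tempting, and the documents do not support them:

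- A reader might infer that the plan rules out adjustment. It does not: the Cox model could carry covariates, and none is listed.
- A reader might infer that the choice between a stratified and an unstratified log-rank test is left open until the data are in. A log-rank test named without strata is naturally read as unstratified, so the open-choice argument fits only the Cox covariates.
- A reader might call the loss modest. The assumed scenarios reach roughly 30 points, so that word is not supported; nor is any single figure in the table.
- A reader might conclude that the analysis as a whole is valid but conservative. That holds for this omission only. Counting limbs while randomising children can cancel or reverse the conservatism.

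It is also fair to object that the fix needs more than one phrase in Section IV.F, because the severity categories are incompletely defined. That stands, and the fix covers it.

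**Conclusion.** The point holds as a conditional loss of efficiency. The primary log-rank test, as written, ignores the factor on which the arms are balanced, and the Cox model's covariates are unspecified. If severity predicts days to re-epithelialization, the test is conservative and less powerful than its stratified counterpart. If it does not, nothing is lost.

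The direction is the same under every model tried in which severity is prognostic. The size is unknown: about nil to roughly 30 power points, depending on how strongly severity shifts healing, the case mix, and whether the SD is read as total or within category. The change should be made because it is nearly free and uses a score already collected at the first visit.

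**What to change.** In Section IV.F, state that the primary log-rank test is stratified by the severity category used at randomisation. State that the Cox model is stratified by the same category and that its hazard ratio is conditional on severity.

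In Section IV.C:

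- Assign every averaged score to a category. The average of two whole-number scores can be 4.5 or 7.5, which fall between categories, and scores 1 and 10 have no category; say whether they are eligible and, if so, where they go.
- Say which category applies when a child's two limbs differ in severity.
- Reconcile the two descriptions of allocation on age. If age is an allocation factor, give its cut-points and add it to the analysis.

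Alongside this, account for both limbs of a child being counted, for example with a variance clustered by child. That is a separate issue and does not add to the size of this one, but stratifying removes conservatism that may partly mask it.

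The cost is wording; no new data are needed. If severity is not prognostic, stratifying costs about 0 to 1 power point: 85.8% to 85.5% with two categories, 85.5% to 85.1% with three, and 84.7% to 83.6% with six severity-by-age cells. The Weibull check showed 2 points.
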